### 8.3. Variables

All data will be extracted from the Premier Hospital database described in section 8.4. Hospital cost data used in this study will be from the hospital perspective reflecting cost incurred to hospitals.

**Table 1. Demographic Variables, Patient Clinical Characteristic Variables, and Hospital Characteristic Variables**

Variable	Role	Operational definition
Age	Patient characteristic and potential confounder	Age will be defined as of the index date and used to assign patients to age groups: 18-34, 35-44, 45-54, 55-64, 65-74 and >75 years, evaluated on the index date.
Gender	Patient characteristic and potential confounder	Distribution of female and male patients and reported as count and percentage, evaluated on the index date.
Race	Patient characteristic and potential confounder	Patients with White, Black, and other/unknown race and reported as count and percentages, evaluated on the index date.
Payer Type	Patient characteristic and potential confounder	Patients with Medicare, Medicaid, commercial, and other/unknown insurance coverage and reported as counts and percentages, evaluated on the index date.
Index Hospitalization Deyo-Charlson Comorbidity Index	Patient characteristic and potential confounder	The Deyo-Charlson Comorbidity Index will be calculated for the index hospitalization .

Variable	Role	Operational definition
Baseline CHADS2	Patient characteristic and potential confounder	The CHADS 2 score evaluated from the available records of the index hospitalization and baseline period will be used to estimate stroke risk. The maximum score is 6. CHADS 2 scores: 0, 1,2, ≥3
Baseline CHADS2-VASc Score	Patient characteristic and potential confounder	The CHADS 2 VASc score evaluated from the available records of the index hospitalization and baseline period will be used to estimate stroke risk. The maximum score is 9. CHADS 2 -VASc scores: 0, 1,2, ≥3
Baseline HAS-BLED Score	Patient characteristic and potential confounder	HAS-BLED score evaluated from the available records of the index hospitalization and baseline period will be used to estimate the risk of MB for patients.
Baseline Prior Bleed	Patient characteristic and potential confounder	Patients with a bleeding diagnosis on hospital records during the baseline period and reported as count and percentage. Bleeding diagnosis will have a breakdown of any, gastrointestinal, and intracranial.
Index Stroke/Transient Ischemic Attack (TIA)	Patient characteristic and potential confounder	Patients with a stroke/TIA diagnosis on hospital records during their index hospitalization and reported as count and percentage.
Baseline Prior Stroke/TIA	Patient characteristic and potential confounder	Patients with a stroke/TIA diagnosis on hospital records during the baseline period and reported as count and percentage.
Index Hospitalization Congestive Heart Failure	Patient characteristic and potential confounder	Patients with a diagnosis on hospital records for congestive heart failure in the index hospitalization and reported as count and percentage.
Index Hospitalization Diabetes	Patient characteristic and potential confounder	Patients with a diagnosis on hospital records for diabetes in the index hospitalization and reported as count and percentage.
Index Hospitalization Hypertension	Patient characteristic and potential confounder	Patients with a diagnosis on hospital records for hypertension in the index hospitalization and reported as count and percentage.
Index Hospitalization Peripheral Vascular Disease	Patient characteristic and potential confounder	Patients with a diagnosis on hospital records for peripheral vascular disease in the index hospitalization and reported as count and percentage.

Variable	Role	Operational definition
Index Hospitalization Pulmonary Disease	Patient characteristic and potential confounder	Patients with a diagnosis on hospital records for pulmonary disease in the index hospitalization and reported as count and percentage.
Index Hospitalization DOAC Dose Strength	Patient characteristic and potential confounder	Patients with apixaban, dabigatran, and rivaroxaban dose strengths of high, low, and unknown during the index hospitalization and reported as count and percentage.
Other Anticoagulants During Index Hospitalization	Patient characteristic and potential confounder	Patients who receive enoxaparin, dalteparin, tinzaparin heparin, and fondaparinux during the index hospitalization and reported as count and percentage.
Index Hospital Geographic Region	Patient characteristic and potential confounder	East North Central, East South Central, Middle Atlantic, Mountain, New England, Pacific, South Atlantic, West North Central, West South Central. Reported as count and percentage
Index Hospital Urban/Rural Status	Patient characteristic and potential confounder	Rural, urban- reported as count and percentage
Index Hospital Teaching Status	Patient characteristic and potential confounder	Yes/No- reported as count and percentage
Index Hospital Bed Size	Patient characteristic and potential confounder	0-99, 100-199, 200-200, 300-399, 400-499, $\geq$ 500- reported as count and percentage

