### **8.9. Strengths and limitations of the research methods**

A key strength is that retrospective analyses provide a better understanding of the study population in real-world clinical practice as compared to the controlled conditions of a clinical trial. Retrospective database studies allow observation of patients who are often under-represented in clinical trials, such as those with comorbidities and the elderly.

Patient data in the Premier Hospital database are only representative of hospital costs and exclude outpatient healthcare utilization and costs not received in a hospital. While the Premier Hospital database contains information from a large number of hospitals across the U.S., it is possible that it may not be representative of the entire U.S. population of NVAF patients. Additionally, patient treatment information and history in the outpatient settings are not available in the Premier Hospital database. Also, hospital readmissions are only captured when patients are readmitted to the same Premier database hospitals. Lastly, billing and coding errors and missing data could potentially occur on database records.

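### Table 1 has no covariate for earlier hospital use, so in the prior-bleed and prior-stroke rows a patient with no captured earlier stay looks the same as one with a clean record

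*Protocol*

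**What the plan says.** Table 1 in Section 8.3 gives the operational definition of each potential confounder. Its rows use three windows.

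- **Index stay only.** The rows for heart failure, diabetes, hypertension, peripheral vascular disease and pulmonary disease, and the Charlson index. The heart failure row is typical: "Patients with a diagnosis on hospital records for congestive heart failure in the index hospitalization and reported as count and percentage".
- **Index stay plus baseline.** CHADS2 and CHADS2-VASc, each "evaluated from the available records of the index hospitalization and baseline period will be used to estimate stroke risk". HAS-BLED uses the same two sources for bleeding risk.
- **Baseline only.** Prior bleed ("Patients with a bleeding diagnosis on hospital records during the baseline period and reported as count and percentage") and, in the same form, prior stroke/TIA.

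Section 8.1 sets the baseline period at 12 months. Section 8.2.1 does not require an earlier stay in the database. Section 8.9 states that "patient treatment information and history in the outpatient settings are not available in the Premier Hospital database", and that readmissions are seen only when the patient returns to the same participating hospitals. It does not draw the matching conclusion for baseline history.

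Section 8.7 plans 1:1 propensity score matching of each comparator with apixaban, followed by a logistic model with the index drug as sole covariate. If too few patients can be matched, a multivariable logistic model replaces it, with covariates described only as key demographics and hospital characteristics.

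**The concern.** With hospital records as the only source, a prior bleed or prior stroke/TIA can be recorded only if the patient had an earlier captured stay. The same applies to the baseline contribution to the three risk scores. A no in these rows therefore mixes two kinds of patient: those whose earlier record shows no event, and those with no earlier record. No Table 1 row separates them.

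Earlier hospital use could matter in two ways. It governs how completely history is recorded, and it plausibly predicts a captured readmission. Recently hospitalized patients tend to be readmitted, and patients who already use a participating hospital may be likelier to return to it. The second way is a judgement, not something the protocol states.

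If earlier hospital use differs between drug cohorts, a propensity score built from Table 1 balances it only so far as it correlates with the listed covariates. Nothing later in the plan picks it up. Any remaining imbalance enters the comparisons of both major-bleeding and all-cause readmission.

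**Working it through.** The protocol states no figure on this point, so there is none to reproduce. The check compares the rows and then sizes the possible effect under stated assumptions.

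**1. Which rows depend on an earlier stay?** This reads the baseline as separate from the index stay, as Table 1's wording implies.

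| Table 1 item | Window | Needs an earlier captured stay? |
|---|---|---|
| Five comorbidity rows, Charlson index | index stay | no |
| CHADS2, CHADS2-VASc, HAS-BLED | index stay + baseline | for the baseline part |
| Prior bleed, prior stroke/TIA | baseline | yes |
| Any earlier stay, or number of stays | not listed | – |

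**2. Effect of an unbalanced earlier stay.** Let a proportion *a* of apixaban and *b* of comparator patients have an earlier stay that multiplies readmission risk by *m*. With no drug effect, the spurious risk ratio is

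RR = [1 + (m − 1)b] / [1 + (m − 1)a].

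All inputs are assumptions: a = 25%, b = 30% or 35%, m = 1.5 or 2.0.

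- b = 30%, m = 1.5: 1.15/1.125 = 1.022
- b = 30%, m = 2.0: 1.30/1.25 = 1.040
- b = 35%, m = 1.5: 1.175/1.125 = 1.044
- b = 35%, m = 2.0: 1.35/1.25 = 1.080

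If b = a, RR = 1. Balance on correlated covariates would pull these values towards 1.

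**3. Effect of history that goes unrecorded.** Let true history be 10% in apixaban and h in the comparator. Let a share c of histories be captured (equal in both cohorts), let history carry an odds ratio of 2-3 for major-bleeding readmission, and let the base risk be 1%. Match on recorded history only. Among patients with nothing recorded, true history remains in h(1 − c)/(1 − hc). For c = 20% this is 0.08/0.98 = 8.2% when h = 10%, and 0.12/0.97 = 12.4% when h = 15%. With an odds ratio of 3, the cohort risks are 1.194% and 1.274%, a spurious odds ratio of 1.068. Over h = 12% or 15% and c = 20% to 80%, the range is 1.004-1.068. With h = 10% in both cohorts it is 1.00.

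**4. Scale for major bleeding.** Section 8.5 assumes 1.4% and a difference of 0.5 points. The sizes in Table 3 are reproduced by 1.4% against 0.9% (for example 2 × 7,137 = 14,274 at 80% power). The planned ratio is therefore 1.4/0.9 = 1.56. On 0.9%, a spurious ratio of 1.022-1.08 is 0.9% × 0.022 = 0.02 points to 0.9% × 0.08 = 0.07 points, against the planned 0.5.

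**5. Scale for all-cause readmission.** Section 6 cites an 18% one-month rate, and Section 8.5 gives at least 30,000 patients per cohort. Take 30,000 pairs, treated as independent. With p the apixaban risk (18%) and p′ = 18% × RR the comparator risk,

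SE(log RR) = √{[(1 − p)/p + (1 − p′)/p′]/30,000} ≈ 0.017.

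- RR 1.022: 0.022/0.0173 = 1.3 SE
- RR 1.044: 0.0435/0.0172 = 2.5 SE
- RR 1.080: 0.077/0.0170 = 4.5 SE

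Fewer matched pairs would lower these multiples.

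**The case against.** **Table 1 does not fix the matching set.** Section 8.7 does not list the propensity score covariates and leaves detailed methods to an analysis plan that is not shown. That plan could add a prior-stay covariate. This stands as far as it goes. But Table 1 is the protocol's only list of potential confounders with definitions, and matching on that list leaves the factor out.

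**The size is assumed throughout.** This stands. No section gives the share of patients with an earlier stay, by drug or overall. A reader might infer that the primary comparison is biased against one drug. The protocol supports neither a direction nor a size.

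**The data limit is disclosed.** Partly. Section 8.9 concedes the lack of outpatient history, but not that an absent record and a clean record are coded alike.

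Two stronger readings are tempting and should not be drawn.

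- *That measuring comorbidities in the index stay alone is an error, or throws away a year of diagnoses.* It is not and does not. Section 8.1 states the split between index and baseline measurement, and the row names follow it. The risk scores carry heart failure, hypertension, diabetes and vascular disease from the baseline period, although CHADS2 and CHADS2-VASc are grouped coarsely with a top class of 3 or more. Pulmonary disease and the Charlson items outside the scores have no look-back, which is a defensible choice.
- *That those rows should be widened to include the baseline period.* This would make six uniformly measured items depend on having an earlier stay, which is the very unevenness at issue.

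**Conclusion.** The point holds in a limited form. The prior-bleed row, the prior-stroke/TIA row and the baseline part of the three risk scores cannot tell a clean earlier record from no record, and Table 1 offers no covariate for earlier hospital use. Bias between cohorts requires that earlier stays or true history differ by drug.

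Under the assumed differences the spurious risk ratio is about 1.02-1.08. For the primary endpoint that is at most about 0.07 of a percentage point against a planned 0.5, so it does not threaten the planned major-bleeding contrast. For all-cause readmission, a secondary objective, a ratio of 1.04 or more could exceed two standard errors at the stated cohort sizes and be read as a drug effect. The change is worth making because it is nearly free, not because bias has been shown.

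**What to change.** Add one row to Table 1, as a potential confounder: number of earlier hospital stays in the database during the 12-month baseline period (0, 1, 2 or more). State that it enters the propensity score, and the multivariable model if that fallback is used. Report its distribution by cohort before matching and its standardized difference after. The table before matching would also show whether earlier stays differ by drug, the one fact needed to judge whether the concern matters.

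Leave the windows of the comorbidity rows and the Charlson index as they are.

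No new data are needed, since 12 months of records are already drawn for the exclusions in Section 8.2.2 and for the risk scores. The cost is one more matching covariate and possibly slightly fewer matched pairs. The covariate balances hospital use and the opportunity to record history. It cannot recover events treated only in outpatient care or outside the database, so Section 8.9 should say that baseline history is limited in this way.

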## 1. LIST OF ABBREVIATIONS

Abbreviation	Definition
AF	Atrial Fibrillation
AFL	Atrial Flutter
CCI	Charlson Comorbidity Index
CHADS 2	Congestive heart failure, Hypertension, Age $\geq$ 75 years, Diabetes mellitus, Stroke
CHADS 2 -VASc	Congestive heart failure, Hypertension, Age $\geq$ 75 years, Diabetes mellitus, Stroke, Vascular disease, Age 65-74 years, Sex category
DOAC	Direct-acting Oral Anticoagulant
HAS-BLED	Hypertension, Abnormal Renal/Liver Function, Stroke, Bleeding History or Predisposition, Labile International Normalized Ratios, Elderly, Drugs/Alcohol
HIPAA	Health Insurance Portability and Accountability Act
ICD-9 CM	International Classification of Diseases, 9th Revision
ICD-10 CM	International Classification of Diseases, 10th Revision
MB	Major Bleeding
NVAF	Nonvalvular Atrial Fibrillation
OAC	Oral Anticoagulant
PSM	Propensity Score Matching

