#### 8.4. Data sources

The data source is the Premier Hospital database, which provides hospital billing information on a patient’s hospital stay as well as information on ICD-9 and ICD-10 codes and current procedural terminology codes. Specifically, the database contains a date-stamped log of all billed items, including medications, laboratory, diagnostic, and therapeutic services, and primary and secondary diagnoses for each patient’s hospitalization. Identifier-linked files provide demographic and payer information. Detailed service-level information for each

hospital day is recorded and this includes details on medication received. Billed items are standardized by the database vendor after the hospital both reviews and consents to the items.

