### 8.7. Data analysis

Means  $\pm$  standard deviations, and medians will be provided for continuous variables. Numbers and percentages will be provided for dichotomous and polychotomous variables. Bivariate comparisons of baseline patient and hospital characteristics and readmission measurements will be provided, with appropriate tests (e.g., ANOVA test, chi-square test) used based on the distribution of the measure. A propensity score matching (PSM) 1:1 technique will be used to control for confounders when comparing each of the OAC cohorts vs. the apixaban cohort. A logistic regression analysis will be carried out on the matched patient cohorts to further evaluate the potential impact of treatment with the different OACs vs. treatment with apixaban on 1-month MB-related and all-cause readmissions. Only the index drug will be the covariate, since other patient characteristics are expected to be similar already after the PSM. Since the patient sample size attribution in the PSM process is not known, if the population sizes are not sufficient after the PSM attrition, a multivariable logistic regression analysis will be carried out to assess the potential impact of treatment with the different OACs compared to treatment with apixaban on 1-month MB-related and all-

cause readmissions, separately. The independent covariates in the regression analyses will include key patient demographics and hospital characteristics. The final list of such covariates will be determined with inputs from the Pfizer team. Additionally, we will carry out a two-part model analysis and a generalized linear model with log transformation and gamma distribution to examine the impact of treatment with the 3 different OACs vs. apixaban on MB-related and all-cause hospital readmission costs. Measurements related to exploratory objectives will be analyzed using descriptive statistics. All data analysis will be executed using statistical software SAS version 9.4.

Detailed methodology for summary and statistical analyses of data collected in this study will be documented in a Statistical Analysis Plan (SAP), which will be dated, filed and maintained by the sponsor. The SAP may modify the plans outlined in the protocol; any major modifications of primary endpoint definitions or their analyses would be reflected in a protocol amendment.

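### Table 1's only separate co-medication row is parenteral anticoagulants; antiplatelets and NSAIDs enter at most through an undefined HAS-BLED item, and gastroprotective drugs not at all

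*Protocol*

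**What the plan says.** Every row of Table 1 (protocol section 8.3) is marked as a potential confounder. Apart from the dose strength of the study drugs themselves, the only medication row concerns injectable anticoagulants: "Patients who receive enoxaparin, dalteparin, tinzaparin heparin, and fondaparinux during the index hospitalization". Antiplatelets, NSAIDs, proton pump inhibitors and H2 blockers are not named anywhere in the protocol.

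Table 1 also lists a bleeding score: "HAS-BLED score evaluated from the available records of the index hospitalization and baseline period will be used to estimate the risk of MB". The abbreviation list expands the last parts of that score as "Labile International Normalized Ratios, Elderly, Drugs/Alcohol". The protocol does not say which drugs count towards it, or whether billed medications feed it.

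Section 8.4 says of the data source that "the database contains a date-stamped log of all billed items, including medications, laboratory, diagnostic, and therapeutic services". Section 8.9 adds the limit that "patient treatment information and history in the outpatient settings are not available in the Premier Hospital database".

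On the analysis, section 8.7 says "A propensity score matching (PSM) 1:1 technique will be used to control for confounders" and then, for the matched outcome model, "Only the index drug will be the covariate, since other patient characteristics are expected to be similar already after the PSM". It gives no covariate list for the propensity score. For the fallback regression it names only demographics and hospital characteristics, and leaves the final list open.

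**The concern.** The primary outcome is a readmission with bleeding as the first-listed diagnosis. Antiplatelets and NSAIDs plausibly raise bleeding risk and gastroprotective drugs plausibly lower it. All three can also mark patients whom a prescriber steers towards one anticoagulant, such as those with coronary disease, a stent or an ulcer history. A variable linked to both drug choice and outcome belongs in the matching.

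The protocol already treats in-hospital co-medication as a confounder, but its list stops at injectable anticoagulants. If the other drugs differ between apixaban and a comparator after matching, part of the estimated anticoagulant effect is a co-medication effect. A model with the index drug alone cannot remove it. These drugs are not among the defined characteristics, so the planned bivariate comparisons would not show the imbalance either.

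**Working it through.** **Coverage in Table 1**

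- *Antiplatelets and NSAIDs:* no row. The only route is one item of HAS-BLED. Two patients with equal totals can differ on that item, because another item makes up the difference.
- *Gastroprotective drugs:* no row, and no HAS-BLED component in the abbreviation list covers them.
- *Reasons for antiplatelet use:* there is a peripheral vascular disease row, and CHADS2-VASc contains vascular disease. That score is grouped as 0, 1, 2 and 3 or more, so a patient who reaches 3 on other items loses the information. There is no coronary disease or stent row. The acute myocardial infarction exclusion does not remove stable coronary disease.
- *Ulcer risk:* prior bleeding has a gastrointestinal breakdown, which is a partial proxy.

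**The plan's own scale**

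Table 3 is reproduced with 1.4% vs 0.9%, two-sided 0.05 and 80% power:

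n per arm = [1.960·√(2·0.0115·0.9885) + 0.842·√(0.014·0.986 + 0.009·0.991)]² / 0.005² = 7,137.

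Doubled, this is 14,274, the tabulated value. The planned contrast is therefore a difference of 0.5 points, or a ratio of 1.4/0.9 = 1.56.

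**Possible size of the bias**

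The documents give no prevalence of use and no effect of these drugs on bleeding, so these inputs are assumptions. With prevalence p_c in the comparator, p_a in the apixaban cohort, and bleeding risk ratio RR for the co-medication:

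bias factor = [1 + p_c(RR − 1)] / [1 + p_a(RR − 1)].

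The spurious difference is (factor − 1) × 1.4%, taking the protocol's 1.4% as the apixaban rate and assuming no true drug effect. The last column is the chance of a significant result showing the comparator as worse, approximately Φ(d/SE − 1.96) with SE = √[2p̄(1 − p̄)/n] and n = 30,000 per arm. The nominal value is 2.5%.

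| p_c vs p_a | RR | Bias factor | Spurious difference | Chance |
|---|---|---|---|---|
| 40% vs 30% | 1.5 | 1.20/1.15 = 1.043 | 0.06 points | 9% |
| 40% vs 30% | 2.0 | 1.40/1.30 = 1.077 | 0.11 points | 20% |
| 45% vs 30% | 2.0 | 1.45/1.30 = 1.115 | 0.16 points | 37% |

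- *Smaller matched sample:* 30,000 is the pre-matching minimum. With an assumed 20,000 per arm the chances are 7%, 14% and 27%.
- *Reversed imbalance (more use with apixaban):* the factors become 0.958, 0.929 and 0.897.
- *Gastroprotective drugs, assumed 40% with apixaban vs 30% with the comparator:* RR 0.8 gives 0.94/0.92 = 1.022; RR 0.6 gives 0.88/0.84 = 1.048. These also invert if the imbalance is reversed.

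**Against the reported and planned effects**

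Section 6 cites earlier odds ratios of 1.2 for dabigatran (p = 0.16) and 1.4 for rivaroxaban (p < 0.01). The outcome is rare, so odds and risk ratios are close.

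- Share of the 0.20 excess in 1.2: 0.043/0.20 to 0.115/0.20, or 22% to 58%.
- Share of the 0.40 excess in 1.4: 11% to 29%.
- Share of the 0.56 excess in the planned ratio: 8% to 21%.

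**The case against.** The strongest reply is that section 8.7 never ties the propensity score to Table 1. It defers detailed methods to an SAP that is not shown, and a propensity model's covariates are often fixed there. A reader might infer from Table 1 that antiplatelets and NSAIDs are not matched at all. The protocol does not establish that: HAS-BLED is a listed confounder and has a drugs item. Vascular disease in CHADS2-VASc, the peripheral vascular row and prior gastrointestinal bleeding are further partial proxies. This part of the reply stands, and it limits the point to drugs that are not *separately* listed. It does not help gastroprotective drugs, which have no route in. Nor does it alter the fact that Table 1 is the confounder list this document fixes.

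A second reply is that the size is assumed throughout. The scenarios need a 10 to 15 point imbalance to survive matching on the listed variables, every spurious difference is below the planned 0.5 points, and the largest share comes from setting the bias against the non-significant 1.2. That is fair, and is why the shares against 1.4 and against the planned contrast are shown too.

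A third reply is that the outcome falls after discharge, when co-medication is unseen, and section 8.9 already discloses the lack of outpatient data. This limits what the fix can achieve. It does not justify leaving out inpatient data that are available.

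**Conclusion.** The point holds as a moderate, inexpensive improvement. The confounder list has one separate co-medication row, the data source can supply the others, and the matched model cannot correct imbalance in what is left out. Residual confounding of the primary comparison is possible. Under the assumed inputs for antiplatelet or NSAID use it is a factor of about 1.04 to 1.12, or about 0.90 to 0.96 in the other direction. That is small beside the planned difference, but in cohorts of this size it is enough to raise the chance of a false significant result.

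A reader might go further and infer that the comparison is biased in favour of apixaban, or that co-medication explains much of the earlier odds ratios. The documents support neither. They give no prevalence, no effect size and no direction.

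**What to change.** Add separate yes/no rows to Table 1 for inpatient use of aspirin, P2Y12 inhibitors, NSAIDs, and proton pump inhibitors or H2 blockers. Take them from billed items up to the first oral anticoagulant dose of the index stay, where dates allow. A flag for any use during the stay could pick up drugs started or stopped because of the anticoagulant chosen, and matching on those can itself introduce bias.

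Enter the flags in all three propensity scores (apixaban against dabigatran, rivaroxaban and warfarin) and in the fallback regression. Report their balance after matching. Keep HAS-BLED as a confounder beside them: it also carries renal and liver function, labile INR and alcohol, which have no rows of their own. State which drugs its drugs item counts and whether billed medications feed it.

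The cost is a few more billing flags, a slightly larger propensity model and possibly some lost matches. The sample size calculation does not change. For patients who receive the anticoagulant soon after admission the look-back within the stay is short. Outpatient use remains unseen, so control is partial, and section 8.9 should say so for co-medication specifically.
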